### 5.5.2 MENQOL related endpoint

- Mean change in MENQOL domain and single item scores from baseline over time

The MENQOL domain scores and single item scores will be analyzed similar to MENQOL total score, as described in Section 5.4.2. Converted scores will be shown in the tables.

### 5.5.3 Body composition related endpoints

- Mean change in body weight from baseline over time
- Mean change in body composition from baseline over time (fat %, fat free mass (FFM), muscle mass, total body water (TBW), bone mass and visceral fat rating)

Weight and body composition measures will be summarized using descriptive statistics by treatment group for each week, as well as absolute changes from baseline to various weeks will be presented. The change from baseline over time in the weight and body composition measures will be shown using line plots for means together with 95% CIs by treatment group.

## 5.6 Safety Analyses

### 5.6.1 Extent of Exposure

The analyses described in this section will be presented for the SAF, the FAS and the BAS. All measures will be presented for weeks 1-12, weeks 13-52 and overall.

Treatment duration will be defined as the number of days from the day of first study drug intake up to and including the day of last study drug intake and will be summarized using descriptive statistics by treatment group.

The extent of exposure to elinzanetant will be summarized as the total amount of study drug intake in grams and the daily dose in mg using descriptive statistics per treatment group.

The compliance (as percentage) will be calculated as:

$$100 * \text{Number of capsules taken} / \text{Number of planned capsules}$$

The number of planned capsules is calculated as:

$$\text{Treatment duration} * 2$$

All capsules, including the placebo capsules, will be counted. For participants who withdraw prematurely from the study drug, compliance will be calculated up to the time of last dose. The compliance will be summarized descriptively by treatment group. In addition, percent of compliance will be categorized into 3 groups, less than 80%, 80 to 120% and greater than 120%, and the categories will be summarized by treatment group.

Treatment duration and extent of exposure and compliance will be calculated and presented twice, once based on the ePRO daily instrument 'Study drug intake documentation' and once based on the eCRF 'Drug Accountability' and 'Drug Exposure' pages. For eDiary based presentation, Weeks 1-12 will be defined as days 1-84 and Weeks 13-52 as days from 85 onwards until last study treatment intake. For eCRF page approach, Weeks 1-12 will be defined from start of study treatment until (T3 visit date -1) and Weeks 13-52 as from T3 visit date until end of study treatment intake. If the date for end of exposure is not available in eCRF, the last day of drug intake from eDiary will be used to determine the end of exposure.

### 5.6.2 Adverse Events

Adverse events (AEs) will be collected from the start of study intervention until the last follow-up. (Serious) Adverse events ((S)AEs) which are related to protocol required study procedures (e.g., (S)AE related to invasive study procedures) will be recorded as (S)AEs from the signing of the ICF (pre-treatment (S)AEs). Any medical occurrences/conditions that begin

in the period between signing Informed consent form (ICF) and the start of study intervention, and which are not related to a protocol-required study procedure, will be recorded on the Medical History/Current Medical Conditions, not as AEs.

All AEs will be summarized by treatment group using the Medical Dictionary for Regulatory Activities (MedDRA) preferred terms (PT) grouped by system organ class (SOC) (the current version at the time of analysis) and classified into pre-treatment, treatment-emergent (TEAE) and post-treatment AEs. Incidences of TEAEs and TESAEs per 100 person-years will be summarized by treatment group. The rate per 100 person-years is calculated as

Rate per 100 person-years = number of subjects / (total drug exposure in years / 100),  
where 365.25 days are taken as one year.

A TEAE is defined as any adverse event occurring or worsening on or after the date of the first dose of study drug up to 14 days after the date of the last dose of study drug. AEs will be flagged as TEAE except for AEs for which there is clear evidence that the AE starts before date of first study drug intake (pre-treatment AEs) or after the date of last study drug intake + 14 days (post-treatment AEs).

If the severity of a previously reported event worsens or if the relationship to study intervention/protocol required procedures changes, two separate events should be reported.

Worsening of an AE is defined as follows:

- AE intensity is worsened (e.g., moderate to severe)
- AE changed to a serious event
- AE ends with death

In case an AE starts before the date of last study drug intake + 14 days and worsens after last study drug intake + 14 days will be considered as two AEs, a TEAE and a post-treatment AE.

Partially missing onset AE date will be imputed following a worst-case approach as described in section [5.1.1](#).

In case of events with different intensity within a participant, the maximum reported intensity will be used. If the same event is considered as both unrelated and related to the study drug within a participant, the event will be reported as related to study drug. If the drug relationship is missing, the event will be considered as being related to the study drug.

The tabulation will follow in principle the Bayer Global Standard Tables catalogue (v4.0 or later). SAEs and Adverse events of special interest (AESI) will be summarized in the same way as described for TEAEs. A separate table summarizing TEAEs that occurred in more than 5% of the participants will be provided.

In addition, participants with a COVID-19 as an adverse event will be listed.

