### 3. Sample Size Determination

Approximately 600 participants will be randomly assigned to study intervention. Of these, 300 participants will be randomly assigned to elinzanetant and the other 300 participants will be randomly assigned to the placebo arm. Assuming a yearly drop-out rate of 30 % and 10% during the months 1-3 and 4-6 in the elinzanetant arm, approximately 210 participants will be available that were treated for 1 year and approximately 240 participants will be available that were treated for at least 6 months.

The number of participants needed for this study is based on the total number of participants needed for the safety evaluation. Following the ICH E1 guideline ([EMA 1995](#)), a total of 1500 participants are required that were exposed to at least one dose of elinzanetant 120 mg. Of these 1500 participants 300-600 should have been treated for at least 6 months and approximately 100 for 1 year. Based on the number of participants that are available from previous phase 1 and phase 2 studies, together with the number of participants that are planned to be enrolled in upcoming phase 3 studies, the number of participants needed for the elinzanetant arm in this study is 300, also taking into account the assumed drop-out described above.

Assuming a screen failure rate of 30% approximately 860 participants need to be enrolled to achieve the required number of 600 randomized participants. Additionally, further participants may be enrolled in case of an exceptionally high drop-out rate due to a trial-continuity issue.

A formal sample size justification was performed for the primary efficacy endpoint using the one-sided two-Sample T-test (equal variance) assuming at least approximate normal distribution. Drop-out rate during the first 3 months is assumed to be 10%. The power with treatment differences (i.e. mean change in frequency of moderate to severe HFs from baseline to Week 12), with N=270 per treatment group and assumed standard deviation are provided in [Table 3-1](#). The data from placebo arm in SWITCH-1 study ([NCT03596762, 2020](#)) was used for assumption of standard deviation.

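### The incidence of TEAEs per 100 person-years is divided by total drug exposure, which does not match the time at risk and understates it for frequent events

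*SAP*

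**What the plan says.** SAP 5.6.2 announces the measure: "Incidences of TEAEs and TESAEs per 100 person-years will be summarized by treatment group". It then gives the formula, "Rate per 100 person-years = number of subjects / (total drug exposure in years / 100"), "where 365.25 days are taken as one year". That the numerator means subjects with the event is implied, not written.

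Total drug exposure in years has no definition of its own. The nearest one is treatment duration in SAP 5.6.1: "the number of days from the day of first study drug intake up to and including the day of last study drug intake". Neither section ends a subject's time at her first event.

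The TEAE window, also in SAP 5.6.2, starts at the first dose and runs "up to 14 days after the date of the last dose of study drug".

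Protocol 9.4.5 makes all safety analyses descriptive. The rates are tabulated by arm, and no between-arm ratio or difference of rates is specified.

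**The concern.** An incidence rate needs a numerator and a denominator that describe the same period at risk. Here they differ in two ways.

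- **Time after the first event.** Once a subject has had the event she cannot enter the numerator again, but she adds exposure until her last dose. This lowers the rate, and more so the more frequent the event.
- **The 14 days after the last dose.** Events in this window count, but the days do not. This raises the rate by roughly the same proportion in every row.

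The study runs for 52 weeks and SAP section 3 sizes it on safety exposure, so rates per person-year will be read as the exposure-adjusted summary of adverse events. For the most frequent rows, a reader who takes the figure as a first-event incidence rate would be misled.

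**Working it through.** **Inputs from SAP section 3.** "300 participants will be randomly assigned to elinzanetant". Drop-out: "Assuming a yearly drop-out rate of 30 % and 10% during the months 1-3 and 4-6 in the elinzanetant arm".

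**The plan's own figures.** Taking the percentages as shares of those randomized, 300 × (1 - 0.20) = 240 and 300 × (1 - 0.30) = 210. These match the SAP: "approximately 240 participants will be available that were treated for at least 6 months", and about 210 for one year.

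**Assumptions not in the documents.** Drop-out is linear between the stated points and the same in placebo. The hazard of a first event is constant, discontinuation is unrelated to events, and the 14 days after the last dose are fully observed. The event incidences are illustrative, because the plan states none.

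**Person-years on drug, one arm.** Retention is 100%, 90%, 80% and 70% at months 0, 3, 6 and 12. The mean fraction of the period on drug is 0.25 × 0.95 + 0.25 × 0.85 + 0.50 × 0.75 = 0.825. Over 364 days this is 0.825 × 364 / 365.25 = 0.822 years per subject, or 246.7 person-years for 300. The uncounted window is 300 × 14 / 365.25 = 11.5 person-years, 4.7% of 246.7.

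**Two rates per row.**
- SAP: 100 × subjects with the event / 246.7.
- First event: 100 × the same subjects / person-years to the first event, or to last dose + 14 days if none. The hazard is solved so that the stated share of subjects has the event by last dose + 14 days.

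| Incidence | Subjects | Years at risk | SAP rate | First-event rate | SAP relative to first-event |
|---|---|---|---|---|---|
| 2% | 6 | 255.2 | 2.43 | 2.35 | +3.5% |
| 5% | 15 | 250.8 | 6.08 | 5.98 | +1.7% |
| 10% | 30 | 243.3 | 12.2 | 12.3 | -1.3% |
| 20% | 60 | 227.9 | 24.3 | 26.3 | -7.6% |
| 30% | 90 | 211.8 | 36.5 | 42.5 | -14.1% |
| 50% | 150 | 176.5 | 60.8 | 85.0 | -28.4% |
| 70% | 210 | 134.5 | 85.1 | 156.2 | -45.5% |

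At 2% and 5% the missing 14 days outweigh the time after the event. By 10% the two are about equal, and above that the time after the event dominates.

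**Early onset.** A simulation with mean onset at 30 days gave 12.0 (SAP) against 12.5 near 10% incidence, and 24.3 against 27.8 near 20%. Early events therefore widen the gap: 1 - 24.3/27.8 is about 13%, compared with 7.6% under a constant hazard.

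**What a reader comparing arms would see.** With the same exposure in both arms, the ratio of SAP rates is the ratio of crude percentages:

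| True first-event ratio | Placebo 5% | 10% | 30% | 50% |
|---|---|---|---|---|
| 2.0 | 1.94 | 1.89 | 1.67 | 1.45 |
| 1.5 | 1.48 | 1.46 | 1.37 | 1.27 |
| 1.0 | 1.00 | 1.00 | 1.00 | 1.00 |
| 0.67 | 0.67 | 0.68 | 0.71 | 0.75 |

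If subjects with events stop drug at different rates, the contrast can move away from 1. In a simulation, 60% of each arm was assigned an event, and 5% of those subjects on placebo and 20% on elinzanetant then stopped. The SAP rates were 70.8 and 76.5, a ratio of 1.08, against a first-event ratio of 1.00. With the arms swapped the ratio would be 70.8/76.5 = 0.93.

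**The case against.** The strongest defence is that the formula is open about its denominator. Subjects per 100 person-years of total exposure is a usable descriptive count, and the SAP does not call it a hazard. The ordinary by-subject tables of TEAEs, SAEs and AESIs do not depend on it. Liver safety already has time to first ALT or ALP elevation with censoring (SAP 5.6.3.4.1). When exposure is equal, the ratio of SAP rates is a risk ratio, and a risk ratio closer to 1 than a hazard ratio is not in itself biased.

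Much of this stands. It limits the point to how the figure is labelled and read, and to the frequent rows. It does not remove the point, because SAP 5.6.2 calls the figure an incidence per person-years and the 14-day mismatch remains under either reading.

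A reader might infer two stronger claims, and the documents support neither.

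- **That rates of all common events are understated.** Protocol 2.3.1 uses common for 1% to 10% of participants (somnolence and fatigue). Across 2% to 10% the net difference under a constant hazard is only +3.5% to -1.3%.
- **That the between-arm ratio is understated.** The SAP plans no such ratio. One formed by the reader is pulled toward 1 under similar discontinuation, so it is understated only if the true ratio exceeds 1. It is unchanged at 1, moves up below 1, and can be inflated when events lead to more stopping on elinzanetant.

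**Conclusion.** The point holds for frequent events. As a first-event incidence rate, the SAP figure is too low by about 7.6% at 20% incidence, rising to 45.5% at 70%, with any TEAE the row most exposed. Rows at 2% to 10% are nearly unaffected under a constant hazard, because the two mismatches offset. That offset is accidental and weakens with early onset.

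Both mismatches can be read directly from SAP 5.6.1 and 5.6.2. Their size rests on the assumed incidences, the hazard shape and the drop-out pattern, which the SAP states for the elinzanetant arm only. The distortion of a by-arm comparison depends on the true ratio and on how often subjects with events stop drug in each arm, so no single direction can be claimed. No efficacy result is involved.

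**What to change.** In SAP 5.6.2, replace the rate definition. For each event row, sum person-time from first dose to the first occurrence of that event or, for a subject without it, to the earlier of last dose + 14 days and end of follow-up. The rate is then subjects with the event / that person-time in years × 100.

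If the total-exposure version is also kept, label it as subjects per 100 person-years of total exposure and extend its denominator to the 14-day TEAE window.

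The dates needed are already collected. The cost is one revised definition and programming of separate person-time for every row, which is more work than a single denominator per arm. Reported rates for frequent events will be higher than under the present formula.

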### **Adverse events of special interest (AESI)**

AESIs will be identified by Standardized MedDRA Query (SMQ) searches, PTs and also via eCRF as further detailed in Section [6.7](#). The following AEs are considered:

1. Any condition triggering close liver observation (as listed in Protocol section 10.5)

2. Somnolence or fatigue
3. Phototoxicity
4. Post-menopausal uterine bleeding (women without hysterectomy are considered)

### 5.6.3 Additional Safety Assessments

#### 5.6.3.1 Physical examination

Weight, hip and waist circumference and waist to hip ratio will be summarized by treatment group for each visit, including change from baseline where appropriate, using descriptive statistics as described in Section 5.1. The absolute values by visit and by treatment group will be shown using boxplots.

#### 5.6.3.2 Vital signs

Vital signs (pulse rate, systolic blood pressure and diastolic blood pressure) will be summarized by treatment group for each visit, including change from baseline where appropriate, using descriptive statistics as described in Section 5.1. The absolute values by visit and by treatment group will be shown using boxplots. In addition, for systolic and diastolic blood pressure the line-plots depicting the mean change from baseline  $\pm 95\%$  CI by treatment group as well as scatter plot (with regression lines) showing blood pressure values at Week 12 and end of treatment (EoT) against baseline by treatment group will be provided.

#### 5.6.3.3 Electrocardiograms

Unscheduled electrocardiograms (ECGs) will be shown in data listings only. Bazett's formula, Fridericia's formula and/or calculations based on linear regression techniques will be shown for corrected QT-interval (QTc), when available.

#### 5.6.3.4 Clinical laboratory

The tabulation of clinical laboratory data will be presented by treatment group for each visit according to the Bayer Global Standard Tables catalogue (version 4.0 or later). It includes:

- Summary statistics of continuous laboratory parameters, and their changes from baseline
- Frequency tables for categorical laboratory parameters

The distribution of laboratory values by treatment group for each visit will be graphically displayed with boxplots. Line plots depicting the mean change from baseline  $\pm 95\%$  CI will be provided for CK, LDH, estradiol, HbA1c, total cholesterol, HDL, LDL, TG and for liver parameters: AST, ALT, ALP, Total bilirubin and INR.

Treatment-emergent (i.e., 14 days from the last drug intake) high and low laboratory abnormalities will be summarized by treatment group. Both scheduled and unscheduled laboratory measurements will be used in the treatment-emergent abnormal laboratory tables.

Central laboratory will be considered for descriptive analysis. Local laboratory measurements will be listed, if available.

#### 5.6.3.4.1 Liver monitoring

The following parameters will be investigated in addition to the standard lab presentations:

- Aspartate aminotransferase (AST) (in U/L),
- Alanine aminotransferase (ALT) (in U/L),
- Alkaline phosphatase (ALP) (in U/L),
- Total bilirubin in serum (TB) (in mg/dL)
- International normalized ratio (INR).

Frequency tables presenting number and percentage of participants by treatment group for baseline and post-baseline (both scheduled and unscheduled measurements can be used) will be presented for the following categorizations (where ULN stands for “Upper Limit of Normal”):

- For ALT and AST, separately:
  - $\geq 1 \times \text{ULN}$ ,  $\geq 3 \times \text{ULN}$ ,  $\geq 5 \times \text{ULN}$ ,  $\geq 8 \times \text{ULN}$ ,  $\geq 10 \times \text{ULN}$ ,  $\geq 20 \times \text{ULN}$
- For ALT and AST combined (if at least one of ALT and AST falls into the category):
  - $\geq 3 \times \text{ULN}$ ,  $\geq 5 \times \text{ULN}$ ,  $\geq 8 \times \text{ULN}$ ,  $\geq 10 \times \text{ULN}$ ,  $\geq 20 \times \text{ULN}$
- For Total bilirubin:
  - $\geq 1 \times \text{ULN}$ ,  $\geq 2 \times \text{ULN}$ ,  $\geq 5 \times \text{ULN}$ ,  $\geq 8 \times \text{ULN}$
- For ALP:
  - $\geq 1.5 \times \text{ULN}$ ,  $\geq 2.0 \times \text{ULN}$ ,  $\geq 3.0 \times \text{ULN}$
- For INR:
  - $\geq 1.5$ ,  $\geq 2$

Frequency tables presenting number and percentage of participants by treatment group for post-baseline will be presented for the following combinations of ALT/AST and Total bilirubin or INR,

*Relative to ULN:*

- ALT or AST  $\geq 3 \times \text{ULN}$  and  $\geq 1.5 \times \text{ULN}$  in Total bilirubin
- ALT or AST  $\geq 3 \times \text{ULN}$  and  $\geq 2 \times \text{ULN}$  in Total bilirubin
- ALT or AST  $\geq 3 \times \text{ULN}$  followed by  $\geq 2 \times \text{ULN}$  in Total bilirubin (measured within 30 days afterwards) (Hy's Law criteria).
- ALT or AST  $\geq 3 \times \text{ULN}$  and  $\geq 1.5$  of INR
- ALT or AST  $\geq 5 \times \text{ULN}$  for more than 2 weeks
- ALT or AST  $\geq 8 \times \text{ULN}$

- ALT or AST  $\geq 3 \times \text{ULN}$  with the appearance of any signs or symptoms on close liver observation eCRF page.
- ALP  $\geq 2 \times \text{ULN}$  and Total Bilirubin  $\geq 2 \times \text{ULN}$

*Relative to baseline (BL):*

- ALT or AST  $\geq 3 \times \text{BL}$  and Total bilirubin  $\geq 2 \times \text{BL}$
- ALT  $\geq 3 \times \text{BL}$  or AST  $\geq 3 \times \text{BL}$
- ALT  $\geq 5 \times \text{BL}$  or AST  $\geq 5 \times \text{BL}$
- ALT or AST  $\geq 2 \times \text{BL}$  and Total bilirubin  $\geq 2 \times \text{BL}$
- ALP  $\geq 2 \times \text{BL}$  and Total bilirubin  $\geq 2 \times \text{BL}$

*Time to event analysis*

Cumulative incidence estimates for the time to first occurrence of ALT  $\geq 3 \times \text{ULN}$  and first occurrence of ALP  $\geq 3 \times \text{ULN}$  will be derived. If no such an increase is observed, the observation is censored at the last visit date. Tables with the number of participants under risk, cumulative number of participants with ALT  $\geq 3 \times \text{ULN}$  and ALP  $\geq 3 \times \text{ULN}$ , and estimated probability for an event including 95% CIs (two-sided) will be presented. Furthermore, cumulative incidence curves will be provided by treatment group. If a participant does not have any post-baseline data, she will be censored at baseline.

*Figures*

Hepatocellular drug-induced liver injury (DILI) screening plot will be displayed to identify cases of possible serious hepatocellular DILI. In the plot each participant is plotted based on their maximum postbaseline Total bilirubin (y-axis) and transaminase values (ALT or AST, whichever is higher). Together with the plot a frequency table for participants in each quadrant (Potential Hy's Law, Cholestasis, Temple's corollary) will be shown.

Cholestatic drug-induced liver injury screening plot will be shown to identify significant ALP elevation in the setting of hepatic dysfunction. Maximum postbaseline Total bilirubin is plotted against maximum postbaseline ALP. Similar to above a frequency table for participants in each quadrant (Total bilirubin  $\geq 2 \times \text{ULN}$  and ALP  $\geq 2 \times \text{ULN}$ , Total bilirubin  $\geq 2 \times \text{ULN}$  and ALP  $< 2 \times \text{ULN}$ , Total bilirubin  $< 2 \times \text{ULN}$  and ALP  $\geq 2 \times \text{ULN}$ ) will be shown.

*Individual participant presentations*

If a participant met close liver observation criteria, a plot for her individual time course in the following laboratory parameters will be presented: 1) ALT, AST, Total bilirubin and ALP relative to ULN over time and 2) absolute values for INR over time. It will be indicated within the plot on which days the study drug was taken (i.e. start and stop dates of treatment intake), in addition all AEs and CM 6 months (182 days) prior to the first onset of close liver observation will be shown in the plot 1. Furthermore, listing will be provided for INR

(absolute values) and for liver-related parameters, i.e. ALT, AST, Total and direct bilirubin, ALP, GGT, CK and LDH (with results relative to ULN).

